5.6.2. Analysis of Secondary Efficacy Variables

Secondary efficacy variables will be analyzed using linear mixed-effect model in the same fashion as the primary analysis for primary endpoint, average CSMS during birch pollen season. Subjects with at least 1 day of post-baseline diary record will be included in the analysis, and only days with observed data (including any available data of daily entries prior to subject discontinuation) will be included in the calculation of average score. Data after rescue will be utilized and data after relevant prohibited medications will be set to missing according to Table 2.

5.6.3. Adjustment for Multiple Comparison

The following multiplicity adjustment approach, a hierarchical procedure, will be used to control overall Type-1 error rate at 0.05 for the primary endpoint and the secondary endpoints. Each hypothesis will be formally tested only if the preceding one is significant at the 2-sided 0.05 significance level. The hierarchical testing order is shown as follows.

- 1. **Primary endpoint**: Daily CSMS, averaged over the duration of the birch pollen season, in subjects who receive a single dose of REGN5713-5714-5715 versus placebo
- 2. TNSS, averaged over the duration of the birch pollen season, in subjects who receive a single dose of REGN5713-5714-5715 versus placebo
- 3. TSS, averaged over the duration of the birch pollen season, in subjects who receive a single dose of REGN5713-5714-5715 versus placebo
- 4. Change from baseline to the end of study in birch SPT mean wheal diameter in subjects who receive a single dose of REGN5713-5714-5715 versus placebo
- 5. Percent change from baseline to the end of study in birch SPT mean wheal diameter in subjects who receive a single dose of REGN5713-5714-5715 versus placebo
- 6. TOSS, averaged over the duration of the birch pollen season, in subjects who receive a single dose of REGN5713-5714-5715 versus placebo
- 7. DMS, averaged over the duration of the birch pollen season, in subjects who receive a single dose of REGN5713-5714-5715 versus placebo

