## 11.4.4. Control of Multiplicity

Type I error rate will be controlled using a hierarchical testing strategy for the primary and key secondary endpoints at the 2-sided significant level of 0.05. The hierarchical order of the primary and key secondary endpoints will be specified in the SAP.

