4.5.2. Secondary Efficacy Variables

The secondary efficacy endpoints are:

- TSS, TNSS, and TOSS, averaged over the duration of the birch pollen season, in subjects who receive a single dose of REGN5713-5714-5715 versus placebo
- DMS, averaged over the duration of the birch pollen season, in subjects who receive a single dose of REGN5713-5714-5715 versus placebo
- Change and percent change from baseline to the end of study in birch SPT mean wheal diameter in subjects who receive a single dose of REGN5713-5714-5715 versus placebo
- The number of "well days" in each of the treatment groups, where the "well days" are defined as days when rescue medication is not utilized and the TSS is $\leq 2/18$

Birch Allergen and Standard Regional Skin Prick Tests

An SPT with birch allergen extract and a regional SPT (such as with dust mites, grasses, ragweed, other trees, including other birch homologous trees [such as alder and oak], mold, cat, and dog) will be performed to assess sensitization status. Skin prick test data may be used to determine the relationship between birch and regional allergen sensitization at baseline and pharmacodynamic effects of REGN5713-5714-5715 to reduce allergic symptoms upon birch pollen allergen challenges. Mean wheal diameter is measured approximately 15 minutes after placement. Aside from the birch skin test requirement for enrollment (which is >=5mm compared to the negative control), a positive response is defined by a mean wheal diameter at least 3 mm greater than a negative control.

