10. APPENDIX

10.1. Summary of Statistical Analyses

10.1.1. Summary of Efficacy Analyses

Endpoint	Analysis Populations	Primary Statistical Method	Supportive/Sensitive Statistical Method	Subgroup Analysis	Other Analyses
Primary Endpoints				·	
Daily CSMS, averaged over the duration of the birch pollen season	FAS	Linear-mixed effect model	N/A	Yes	Plot
Secondary Endpoints					
TSS, TNSS and TOSS averaged over the duration of the birch pollen season	FAS	Linear-mixed effect model	N/A	No	Plot
DMS, averaged over the duration of the birch pollen season	FAS	Linear mixed effect model	N/A	No	Plot
Change and percent change from baseline to the end of study in birch SPT mean wheal diameter	FAS	Linear mixed effect model	N/A	No	Plot
The number of "well days" in each of the treatment groups,	FAS	Linear mixed effect model	N/A	No	Plot

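### Well days is analysed as a raw count with no denominator or missing-day rule, and the SAP does not say what its p-value means outside the testing hierarchy

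*SAP*

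**What the plan says.** **The endpoint.** Protocol 4.2 and SAP 4.5.2 both list the number of well days as a secondary endpoint. Well days "are defined as days when rescue medication is not utilized and the TSS is" at most 2 out of 18. The definition gives no denominator and names no time window; I read it as the birch pollen season, as for the other diary endpoints.

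**The analysis.** SAP 5.6.2 states: "Secondary efficacy variables will be analyzed using linear mixed-effect model in the same fashion as the primary analysis". The table in SAP 10.1.1 confirms a linear mixed model on the FAS for the number of well days, with no supportive or sensitivity method.

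**Missing days.** In SAP 4.5.1, TNSS, TOSS and DMS are averaged over observed in-season days, and TSS and CSMS are sums of those averages. SAP 5.6.2 restricts secondary variables to days with data, but words the rule for an average score. It also sets data after relevant prohibited medication to missing. SAP 6.3 sends the reader to 4.5.1 and 4.5.2 for missing-data rules, and neither has one for well days.

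**Multiplicity.** SAP 5.6.3 says its procedure will "control overall Type-1 error rate at 0.05 for the primary endpoint and the secondary endpoints" and orders seven tests: CSMS, TNSS, TSS, SPT change, SPT percent change, TOSS and DMS. Protocol 11.4.4 is narrower. It plans a "hierarchical testing strategy for the primary and key secondary endpoints at the 2-sided significant level of 0.05" and leaves the order to the SAP.

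**The concern.** An average over observed days adjusts itself when diary days are lost, because numerator and denominator shrink together. A count does not. An unrecorded day adds nothing to it, which has the same effect as recording the day as not well.

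The plan expects such days. SAP 2.3 assumes 20% dropout during the season. Table 2 of SAP 5.6.1 removes data after systemic steroids or Type 2 biologics. SAP 3.1 says TNSS, TOSS and DMS are completed in sequence, so a diary abandoned partway leaves a day that cannot be classified. It is not stated whether an FAS subject with no classifiable day scores zero or is left out.

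At stake is the size and direction of a patient-facing secondary result. Equal loss in both arms shrinks the difference, and unequal loss can create one. The smaller issue is interpretation: the analysis will produce a p-value, and the SAP does not say whether that p-value carries any claim.

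**Working it through.** **1. The plan's own figures.** The documents give no figure for well days. The inputs that bear on it are the sample size and dropout in SAP 2.3: 120 evaluable per arm, difference 1.9, SD 4.5, two-sided 0.05.
- Standard error = 4.5 × √(2/120) = 0.581; 1.9/0.581 = 3.27; 3.27 − 1.96 = 1.31, so power is 0.905 (0.903 with the noncentral t). The stated 90% reproduces.
- 120/(1 − 0.20) = 150 per arm. This reproduces too.

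**2. Expected count.** Expected count = D × p × c, where D is days in season, p the true share of well days and c the share of days recorded. The documents give neither D nor p, so both are assumptions, shown over a range.

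| D | p | full diary | 90% | 80% | stops mid-season |
|---|---|---|---|---|---|
| 20 | 0.3 | 6.0 | 5.4 | 4.8 | 3.0 |
| 20 | 0.5 | 10.0 | 9.0 | 8.0 | 5.0 |
| 30 | 0.3 | 9.0 | 8.1 | 7.2 | 4.5 |
| 30 | 0.5 | 15.0 | 13.5 | 12.0 | 7.5 |
| 60 | 0.3 | 18.0 | 16.2 | 14.4 | 9.0 |
| 60 | 0.5 | 30.0 | 27.0 | 24.0 | 15.0 |

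The count divided by recorded days has expectation p in every cell, provided unrecorded days resemble recorded ones.

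**3. The plan's 20% dropout (D = 30, p = 0.5).** If those subjects stop halfway on average, the arm mean is 0.80 × 15.0 + 0.20 × 7.5 = 13.5 instead of 15.0. The limits are 0.80 × 15.0 = 12.0 (stopping right at the start) and 15.0 (stopping at the end).

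**4. Equal loss dilutes.** Take assumed shares of 50% and 40% over 30 days. Full diaries give 15.0 − 12.0 = 3.0 days. At 80% completion in both arms the difference is 12.0 − 9.6 = 2.4.

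**5. Unequal loss biases.** With the same 50% share in both arms, completion of 90% in one and 80% in the other gives 13.5 − 12.0 = 1.5 days with no true difference.

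A simulation shows what this does to the test. Assumptions: 150 per arm, 30 days, individual shares averaging 40%, days missing at random, no true difference, 4,000 trials per row, and a two-sample t-test standing in for the mixed model.

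| Missing days, arm A v arm B | raw count, p<0.05 | proportion of recorded days, p<0.05 |
|---|---|---|
| 10% v 10% | 0.05 | 0.05 |
| 5% v 10% | 0.10 | 0.05 |
| 5% v 15% | 0.31 | 0.05 |
| 5% v 25% | 0.87 | 0.05 |

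**6. Multiplicity.** Comparing SAP 4.5.2 with 5.6.3, every secondary efficacy endpoint has a step except well days. The seven-step fixed sequence holds 0.05. If a well-days p<0.05 outside it were read as confirmatory, the error rate under the global null would be 1 − 0.95² = 0.0975 with independent tests, falling to 0.070 at correlation 0.9.

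**The case against.** **On multiplicity, the defence is largely right.** Protocol 11.4.4 promises control only for the primary and key secondary endpoints, and the SAP's list can be read as naming them. The literal SAP wording cannot be meant in full, since adverse events, serum concentration and ADA are also secondary endpoints and are properly left out. Protocol 3.2.1 even calls well days an exploratory objective, though under its secondary heading. The SAP adds: "Each hypothesis will be formally tested only if the preceding one is significant at the 2-sided 0.05 significance level". An endpoint outside the order thus has no formal test. What remains is a dropped qualifier and an undefined status for one p-value.

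**On season length,** a reader might infer that different local seasons bias the comparison, because they cap the count differently. The documents do not support that. Allocation is randomised and stratified by North America versus Europe, and the model carries region as a fixed effect and pollen region as a random effect. Season length mainly adds noise, part of which the model absorbs.

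**On missed days,** a reader might infer that each one lowers the count. It does so only if that day would have been well; the statement is exact for the expected count. No figure in the documents shows that completion will differ by arm, so the bias is conditional.

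**On prohibited medication,** treating later days as not well resembles the composite approach used for the primary endpoint. That may be a sensible choice, but SAP 5.6.2 says missing, not unfavourable, so the effect is undeclared.

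**Conclusion.** The concern holds for the count. As written, unrecorded, partly recorded and set-to-missing days act as not-well days. No estimand says this is intended, since Table 1 of the SAP covers only the primary endpoint, and the other diary endpoints are handled differently. In the 30-day, 50% illustration, 80% completion costs 3.0 of 15.0 expected well days, and a gap of 90% versus 80% produces a 1.5-day difference from nothing. These sizes rest on an assumed season length, well-day share and pattern of missingness. Bias between arms requires unequal completion; with equal completion the harm is dilution and noise.

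On multiplicity the finding is one of wording. It might be inferred that the omission breaks the hierarchy. It does not: type I error for the seven listed tests is unaffected, and the 0.070 to 0.0975 range applies only if someone treats the unlisted p-value as confirmatory, which no passage proposes.

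Overall this is a worthwhile improvement to a secondary endpoint. It does not touch the primary analysis.

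**What to change.** **Analysis of well days.**
- Make the main analysis the proportion of observed in-season diary days that are well days, counting only days with TNSS, TOSS and DMS all complete. A count model with log observed days as offset is an alternative.
- State the time window, how partial days are handled, what happens to a subject with no complete day, and whether days after relevant prohibited medication leave the denominator or stay in it as not well.
- Keep the raw count as a supportive summary.

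**Multiplicity.** Either add well days as step 8, last in the sequence, which uses no alpha and leaves steps 1 to 7 unchanged; or limit the claim in SAP 5.6.3 to key secondary endpoints, as the protocol does, and label the well-days p-value nominal.

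**Cost.** No new data are needed, but this is more than a wording edit. Protocol 4.2 defines a number of days, so the change must be declared in SAP 1.2.3, which now records only the removal of the per-protocol set. A proportion assumes unrecorded days resemble recorded ones, so a subject who stops before the pollen peak may look too well. It also gives a short diary the same weight as a full one unless the analysis is weighted or uses the offset.

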5.6.4. Subgroup Analysis

Subgroups described in Section 3.5 for the primary endpoint will be summarized. Treatment difference and its 95% confidence interval in subgroups of subjects will be presented in forest plots.

5.6.5. Analysis of Exploratory Efficacy Variables

For continuous exploratory efficacy variables, e.g. average ACQ-5 and change and percent change in SPT mean wheal diameter for birch homologous/cross-reactive allergens, they will be analyzed by using a linear mixed effects model similar to the analyses of primary endpoint.

For categorical exploratory variables, e.g. PFASQ and PGI-S, only descriptive summary will be provided.

For endpoints related to biomarker, e.g. serum total IgE, serum sIgE for birch and Bet v 1, analysis method will be detailed in section 5.11.

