# 2.3. Exploratory Objectives

The exploratory objectives are:

- To assess asthma control as measured by the asthma control questionnaire (ACQ-5)
- To assess quality of life as measured by the rhinoconjunctivitis quality of life questionnaire (RQLQ [S])
- To evaluate the reduction in early allergic response to birch homologous allergens (alder and oak) as measured by SPT mean wheal diameter
- To assess the relationship between allergy sensitization status to Bet v 1 or birch pollen at screening (as measured by serum allergen specific-IgE [sIgE]) and clinical response to REGN5713-5714-5715 treatment
- To assess serum sIgE levels against Bet v 1 and birch pollen during birch pollen season to evaluate the relationship between the response to REGN5713-5714-5715 and change in sIgE levels in-season
- To assess the inhibitory effect of REGN5713-5714-5715 on the binding of endogenous serum IgE to birch allergen in an in vitro assay; to assess whether the degree of inhibition correlates with clinical improvement
- To assess sIgE levels against other allergens (eg, Bet v 2, alder and oak) at screening and to evaluate the relationship between response to REGN5713-5714-5715 and polyallergic status

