#### 7.2.1. Inclusion Criteria

A subject must meet the following criteria to be eligible for inclusion in the study:

- 1. Generally healthy men and women 18 years of age and older at the time of screening
- 2. Documented or subject-reported history of birch pollen-triggered allergic rhinitis symptoms, with or without conjunctivitis, for at least 2 years
- 3. Positive SPT with birch pollen extract (ie, mean wheal diameter at least 5 mm greater than a negative control) in the screening period
- 4. Positive sIgE tests for birch pollen and Bet v 1 (ie,  $\geq 0.7$  kUa/L) in the screening period
- 5. Willing and able to comply with clinic visits and study-related procedures
- 6. Provide informed consent signed by study subject or legally acceptable representative
- 7. Able to understand and complete study-related questionnaires

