## 8.5. Method of Treatment Assignment

Subjects will be randomized according to a central randomization scheme provided by interactive response technology (IRT) to the designated study pharmacist (or qualified designee) as per Table 1.

Subjects will be randomized 1:1 as below (refer to Section 8.1 for more details):

- REGN5713-5714-5715
- Matching placebo

Randomization will be stratified based on the following:

- Serum specific birch pollen IgE levels at screening (<17.5 kUa/L versus  $\geq$ 17.5 kUa/L)
- In North America only: Serum specific oak pollen IgE levels at screening (<0.7 kUa/L versus ≥0.7 kUa/L)
- Geographical region (North America versus Europe)

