#### 9.2.3. Birch Allergen and Standard Regional Skin Prick Tests

An SPT with birch allergen extract and a regional SPT (such as with dust mites, grasses, other trees, including other birch homologous trees [such as alder and oak], cat, and dog) will be performed to assess sensitization status. Skin prick test data may be used to determine the relationship between birch and regional allergen sensitization at baseline and pharmacodynamic effects of REGN5713-5714-5715 to reduce allergic symptoms upon birch pollen allergen challenges. Mean wheal diameter is measured approximately 15 minutes after placement. Aside from the birch skin test requirement for enrollment, a positive response is defined by a mean wheal diameter at least 3 mm greater than a negative control.

For patients who enroll in the study, SPT will be performed as noted in Table 1 and the mean wheal diameters will be used to assess clinical responses to treatment. The allergens used for SPT will include birch pollen and 1 or 2 additional related homologous tree allergens.

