3.1. The Full Analysis Set (FAS)

The full analysis set (FAS) includes all randomized subjects who had at least 1 e-diary entry with symptoms or medication score recorded during the birch pollen season; it is based on the treatment allocated (as randomized). Since the TNSS, TOSS and DMS will be completed sequentially, all randomized subjects with at lease 1 TNSS e-diary entry will be included in FAS. Efficacy endpoints will be analyzed using the FAS.

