4.5.3. Exploratory Efficacy Variables

Exploratory efficacy endpoints include:

- RQLQ (S), averaged over the duration of the birch pollen season, for REGN5713-5714- 5715 versus placebo
- ACQ-5, averaged over the duration of the birch pollen season, for REGN5713-5714-5715 versus placebo (only for patients with asthma)
- Change and percent change from baseline to the end of study in SPT mean wheal diameter for birch homologous/cross-reactive allergens in REGN5713-5714-5715 versus placebo
- Baseline allergen-specific IgE levels and correlation with average CSMS, TSS, TNSS, TOSS, DMS during birch pollen season
- Number of baseline sensitizations to other allergens (poly/mono-sensitization status, based on allergen-specific IgE levels) and correlation with CSMS, TSS, TNSS, TOSS, and DMS, averaged over the duration of the birch pollen season
- Baseline serum antibody levels and correlation with CSMS, TSS, TNSS, TOSS, and DMS, averaged over the duration of the birch pollen season

Regeneron Pharmaceuticals, Inc. Statistical Analysis Plan

- To assess the reduction in PFAS and related symptoms, as measured by PFASQ, from baseline to end of study
- To assess patient rating of severity of seasonal allergy symptoms, as measured by PGI-S, from baseline to end of study

Standardized Rhinoconjunctivitis Quality of Life Questionnaire [RQLQ (S)]

The RQLQ (S) has 28 questions in 7 domains: activity limitation, sleep problems, nose symptoms, eye symptoms, non-nose/eye symptoms, practical problems, and emotional function. There are 3 subject-specific questions in the activity domain that allow subjects to select 3 activities in which they are most limited by their rhinoconjunctivitis. Subjects recall how bothered they have been by their rhinoconjunctivitis during the previous week and respond to each question on a 7-point scale (0 [not impaired at all] to 6 [severely impaired]). The overall RQLQ (S) score is the mean of all 28 responses, and the individual domain scores are the means of the items in those domains (Juniper, 1991). The RQLQ (S) will be recorded using an e-diary.

Asthma Control Questionnaire

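### Percent change in homologous-tree skin-test wheal has no rule for zero or sub-threshold baselines, although only a birch wheal is required at entry (minor, exploratory)

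*SAP*

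**What the plan says.** The endpoint in SAP 4.5.3 is "Change and percent change from baseline to the end of study in SPT mean wheal diameter for birch homologous/cross-reactive allergens". SAP 5.6.5 lists "change and percent change in SPT mean wheal diameter for birch homologous/cross-reactive allergens" among the continuous variables to be analysed with a mixed model like that of the primary endpoint, which contains treatment, the stratification factors and pollen region, and no baseline wheal. SAP 3.1 states: "Efficacy endpoints will be analyzed using the FAS". The FAS is defined by e-diary entries during the birch season, not by skin-test status.

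The allergens are not fixed. Protocol 2.3 refers to "birch homologous allergens (alder and oak) as measured by SPT mean wheal diameter". Protocol 9.2.3 says: "The allergens used for SPT will include birch pollen and 1 or 2 additional related homologous tree allergens". SAP 3.5 lists only alder and grey alder as birch-related for SPT. SAP 5.6.5 names no tree.

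Protocol 7.2.1 requires a birch wheal at least 5 mm above negative control and sIgE of at least 0.7 kUa/L to birch pollen and Bet v 1. It sets no condition on alder or oak. Protocol 8.5 stratifies North American subjects by "Serum specific oak pollen IgE levels at screening", below versus at or above 0.7 kUa/L. For tests other than the birch entry test, SAP 4.5.2 says that "a positive response is defined by a mean wheal diameter at least 3 mm greater than a negative control". That limit classifies sensitisation; it does not restrict any analysis.

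**The concern.** For birch, the entry criterion keeps every baseline wheal well away from zero, so change and percent change can both be scored. The same two measures are then carried over to allergens for which nothing keeps the baseline away from zero.

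At 0 mm, percent change has no value and change in mm cannot be negative. Just above 0 mm, percent change is mostly measurement noise. Standard software would drop the undefined values without comment, so the two measures would describe different sets of subjects, and the percent-change set would be defined by whether a trace wheal happened to be recorded.

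At stake is the exploratory question whether blocking Bet v 1 also lowers the skin response to cross-reactive trees, which Protocol 1.3 lists among the potential advantages of the approach. If the rule stays open, the subset and the zero-baseline handling could also be chosen after unblinding.

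**Working it through.** **Plan's own figure.** The documents give no sample size, SD or expected effect for this endpoint. The figure borrowed here is the 120 evaluable subjects per arm in SAP 2.3. It reproduces: difference 1.9, SD 4.5, two-sided 0.05, two-sample t-test, 120 per arm gives 90.3% power (stated 90%).

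**Search for a rule.** SAP 5 says that missing baselines are not imputed. SAP 6.2 substitutes LLOQ/2 in laboratory safety and biomarker data. SAP 6.3 refers efficacy missing-data rules to 4.5.1 and 4.5.2, which give none for SPT. Appendix 10.1.1 omits exploratory endpoints. None covers a zero or sub-threshold wheal.

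**Arithmetic of the scale.** Percent change = 100 × (end − baseline) / baseline.

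| Baseline (mm) | Effect of a 2 mm rise |
|---|---|
| 0 | undefined |
| 0.5 | +400% |
| 1 | +200% |
| 3 | +67% |
| 5 | +40% |

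The largest possible fall is −100% at every baseline above zero.

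**Dilution in mm.** Let p be the share with no true homologous wheal, and suppose their mean change does not differ by arm. Then difference in all ≈ (1 − p) × difference in reactive subjects. With an assumed mean wheal of 6 mm and a 20% reduction, the reactive difference is 0.20 × 6 = 1.2 mm. For p = 10%, 30% and 50%: 0.9 × 1.2 = 1.08, 0.7 × 1.2 = 0.84, 0.5 × 1.2 = 0.60 mm.

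**Simulation.** All inputs except 120 per arm are assumptions: reactive wheal 6 (SD 2) mm net of control, 1 mm measurement error at each test, floor at 0, rounding to 0.5 mm, two-sample t-tests, 1,500 trials per setting, true reduction 20%.

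| Quantity | p = 10% | p = 30% | p = 50% |
|---|---|---|---|
| Percent change undefined | 6% | 18% | 30% |
| mm difference, all | 1.08 | 0.84 | 0.60 |
| mm difference, baseline ≥3 mm | 1.25 | 1.25 | 1.25 |
| Power, mm change, all | about 100% | 99.7% | 96% |
| Power, percent change, all above 0 mm | about 92% | about 67% | about 37% |
| Power, percent change, baseline ≥3 mm | about 100% | 99.9% | 98% |

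The positives-only difference exceeds 1.2 mm because the 3 mm limit selects larger wheals. Repeat runs moved the mm differences by about 0.01 and the percent-change powers by a point or two. The power levels depend on the variance assumptions, so the contrast between rows matters more than any single value.

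**Larger effects.** At a 40% reduction and p = 50%, percent-change power is about 89% against about 100% in baseline positives. At 60% to 70% it is about 99% or more even with p = 50%.

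**The case against.** The strongest reply is that little may be affected. Every subject is Bet v 1 positive with a clear birch wheal, and Protocol 1.1 cites strong inhibition by birch pollen of IgE binding to alder, hazel and oak extracts, so alder reactivity may be common. The oak stratum is a serum measure, used only in North America, and says nothing about alder. This stands: p is unknown, and the 30% and 50% scenarios have no anchor for alder.

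Second, analysing everyone is a legitimate choice for change in mm. It is defined for all subjects with both tests. Protocol 3.2.1 notes that sIgE rises in season, so placebo subjects negative at baseline might become reactive while treated subjects do not. This also stands, and it is a reason to keep the all-FAS mm result.

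Third, Protocol 5.6 counts SPT among biomarker variables, so the LLOQ/2 convention might be thought to apply. It does not help: SAP 4.9 does not list SPT, and no quantification limit is given for a wheal.

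A reader might infer that subjects with a 1 to 2 mm wheal cannot improve, that power for mm change suffers, or that a real cross-reactive effect would generally be missed. The first is wrong, because 2 mm can fall to 0. The second is not borne out: mm power stays at about 96% or more in the scenarios above. The third needs both a weak effect and a large non-reactive share. Protocol 1.3 reports placebo-adjusted birch skin-test reductions of about 66% to 78%, and at that size the power loss disappears. Those figures are titration AUCs for birch, so they are only a guide, and homologue effects may be smaller.

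**Conclusion.** The gap is real and minor. Following the text, percent change cannot be computed at a 0 mm baseline and is unstable just above it, and the two measures would use different subjects. That much is arithmetic. The size rests on assumptions. The mm estimate is diluted roughly by the factor (1 − p) with little effect on power. Percent-change power falls materially only if the true reduction is modest and p is substantial.

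It would go too far to say that the trial's efficacy conclusions are at risk. The endpoint is exploratory, lies outside the testing hierarchy in SAP 5.6.3 and carries no power claim. A baseline-positive analysis could still be run later from the collected data, but it would then not be prespecified.

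**What to change.** In SAP 4.5.3 and 5.6.5:

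- Name the homologous allergens to be analysed, and reconcile Protocol 2.3 (alder and oak) with SAP 3.5 (alder and grey alder).
- For each allergen, analyse percent change, and report change in mm, in FAS subjects whose baseline wheal to that allergen is at least 3 mm above negative control.
- Add baseline wheal as a covariate, as Protocol 11.4.8 does for birch.
- State the number analysed per arm for each allergen and measure.
- Keep change in mm in all FAS subjects as a supportive result, and list baseline-negative subjects separately.

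The cost is a few lines of SAP text and no new data. The restriction uses a baseline characteristic, so it keeps the comparison between randomised arms. The downside is fewer subjects in an exploratory analysis: in the scenarios above about 84%, 65% and 46% of subjects would qualify.
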